10.3.1. Causality

The investigator must determine the relationship between the administration of IPs (POM, DARA, or LD-Dex) and the occurrence of an AE/SAE as Not Suspected or Suspected as defined below:

Not suspected: Means a causal relationship of the adverse event to IP (POM, DARA, or LD-Dex) administration is unlikely or remote, or other medications, therapeutic interventions, or underlying conditions provide a sufficient explanation for the observed event.

Suspected: Means there is a reasonable possibility that the administration of IP (POM, DARA, or LD-Dex) caused the adverse event.

‘Reasonable possibility’ means there is evidence to suggest a causal relationship between the IP and the adverse event.

Causality should be assessed and provided for every AE/SAE based on currently available information. Causality is to be reassessed and provided as additional information becomes available.

If an event is assessed as suspected of being related to a comparator, ancillary, or additional IP that has not been manufactured or provided by Janssen, please provide the name of the manufacturer when reporting the event.

10.3.2. Duration

For both AEs and SAEs, the investigator will provide a record of the start and stop dates of the event.

10.3.3. Action Taken

The investigator will report the action taken with IPs (POM, DARA, or LD-Dex) as a result of an AE or SAE, as applicable (eg, discontinuation or reduction of IP, as appropriate) and report if concomitant and/or additional treatments were given for the event.

10.3.4. Outcome

All SAEs that have not resolved upon discontinuation of the subject's participation in the study must be followed until recovered, recovered with sequelae, not recovered (death due to another cause), or death (due to the SAE).

10.3.5. Abnormal Laboratory Values

An abnormal laboratory value is considered to be an AE if the abnormality:

- results in discontinuation from the study;
- requires treatment, modification/ interruption of IPs (POM, DARA, or LD-Dex) dose, or any other therapeutic intervention; or
- is judged to be of significant clinical importance.

Regardless of severity grade, only laboratory abnormalities that fulfill a seriousness criterion need to be documented as a serious adverse event.

If a laboratory abnormality is one component of a diagnosis or syndrome, then only the diagnosis or syndrome should be recorded on the AE page/screen of the CRF. If the abnormality was not a part of a diagnosis or syndrome, then the laboratory abnormality should be recorded as the AE.

10.4. Adverse Events of Special Interest

Adverse events of special interest are events that Janssen Scientific Affairs, LLC is actively monitoring as a result of a previously identified signal (even if non-serious). These adverse events are:

- Infusion reactions: \geq grade 3
- Infections: \geq grade 4
- Cytopenias: \geq grade 4
- Hepatitis B Reactivation
- Other malignancies

Any Adverse Event of Special Interest that is to be reported to the Janssen should be recorded on a Serious Adverse Event Report Form and be reported to the Janssen within **24 hours of knowledge of the event**.

10.5. Individual Case Safety Report (ICSR)

A valid ICSR must contain the four minimum criteria required to meet regulatory reporting requirements.

- an identifiable subject (but not disclosing personal information such as the subject's name, initials or address)
- an identifiable reporter (investigational site)

- a Janssen medicinal product
- an adverse event, outcome, or certain special situations

The minimum information required is:

- suspected Janssen medicinal product (doses, indication)
- date of therapy (start and end date, if available)
- batch or lot number, if available
- subject details (subject ID and country)
- gender
- age at AE onset
- reporter ID
- adverse event detail (AE verbatim in English), onset date, relatedness, causality, action taken, outcome, (if available)
- Janssen protocol ID

10.6. Serious Adverse Event (SAE)

A serious adverse event based on ICH and EU Guidelines on Pharmacovigilance for Medicinal Products for Human Use is any untoward medical occurrence that at any dose:

- Results in death
- Is life-threatening
- (The subject was at risk of death at the time of the event. It does not refer to an event that hypothetically might have caused death if it were more severe.)
- Requires inpatient hospitalization or prolongation of existing hospitalization
- Results in persistent or significant disability/incapacity
- Is a congenital anomaly/birth defect
- Is a suspected transmission of any infectious agent via a medicinal product
- Is medically important*

*Medical and scientific judgment should be exercised in deciding whether expedited reporting is also appropriate in other situations, such as important medical events that may not be immediately life threatening or result in death or hospitalization but may jeopardize the subject or may require intervention to prevent one of the other outcomes listed in the definition above. These should usually be considered serious.

NOTE: DEATH FOR ANY REASON SHOULD BE REPORTED AS A SERIOUS ADVERSE EVENT.

10.6.1. Hospitalization

For reports of hospitalization, it is the sign, symptom or diagnosis which led to the hospitalization that is the serious event for which details must be provided.

Any event requiring hospitalization or prolongation of hospitalization that occurs during the study must be reported as a serious adverse event, except hospitalizations for the following:

- Hospitalizations not intended to treat an acute illness or adverse event (e.g., social reasons such as pending placement in long-term care facility)
- Surgery or procedure planned before entry into the study. [Note: Hospitalizations that were planned before the start of data collection and where the underlying condition for which the hospitalization was planned has not worsened will not be considered serious adverse events. Any adverse event that results in a prolongation of the originally planned hospitalization is to be reported as a new serious adverse event.]
- [For convenience the investigator may choose to hospitalize the subject for the duration of the treatment period.]

10.6.2. Life-Threatening Conditions

Disease progression should not be recorded as an adverse event or serious adverse event term; instead, signs and symptoms of clinical sequelae resulting from disease progression/lack of efficacy will be reported if they fulfill the serious adverse event definition.

10.7. Unlisted (Unexpected) Adverse Event/Reference Safety Information

An adverse event is considered unlisted if the nature or severity is not consistent with the applicable product reference safety information. For a medicinal product(s) with a marketing authorization, the expectedness of an adverse event will be determined by whether or not it is listed in the applicable product information.

<http://www.darzalex.com/shared/product/darzalex/darzalex-prescribing-information.pdf>

For DARZALEX Faspro (daratumumab and hyaluronidase-fihj), the expectedness of an adverse event will be determined by whether or not it is listed in the Investigator's Brochure.

10.8. Special Reporting Situations

Safety events of interest for a Janssen medicinal product that require expediting reporting and/or safety evaluation include, but are not limited to:

- Drug exposure during pregnancy (maternal and paternal)*
- Suspected transmission of any infectious agent via administration of a medicinal product*

*Reports of these events should be recorded on a Serious Adverse Event Report Form and be reported to Janssen Scientific Affairs, LLC **within 24 hours of becoming aware of the event.**

- Overdose of a Janssen medicinal product
- Exposure to a Janssen medicinal product from breastfeeding
- Suspected abuse/misuse of a Janssen medicinal product
- Inadvertent or accidental exposure to a Janssen medicinal product

- Any failure of expected pharmacological action (i.e., lack of effect) of a Janssen medicinal product
- Medication error involving a Janssen medicinal product (with or without patient exposure to the Janssen medicinal product, e.g., name confusion)
-
- Unexpected therapeutic or clinical benefit from use of a Janssen medicinal product

These safety events may not meet the definition of an adverse event; however, from a Janssen Scientific Affairs, LLC perspective, they are treated in the same manner as adverse events. Special situations should be recorded on the Adverse Event page of the CRF.

Any special situation that meets the criteria of a serious adverse event should be recorded on a Serious Adverse Event Report Form and be reported to Janssen Scientific Affairs, LLC within 24 hours of becoming aware of the event.

Maintenance of Safety Information

All safety data should be maintained in a clinical database in a retrievable format. The PRINCIPAL INVESTIGATOR shall provide all adverse events, both serious and non-serious, in report format. However, in certain circumstances more frequent provision of safety data may be necessary, e.g. to fulfill a regulatory request, and as such the data shall be made available within a reasonable timeframe at Janssen Scientific Affairs, LLC request.

Procedures for Reporting Safety Data and Product Quality Complaints (PQCs) for Janssen Medicinal Products to Janssen Scientific Affairs, LLC

All adverse events and special situations, whether serious or non-serious, related or not related, following exposure to a Janssen medicinal product are to be documented by the investigator and recorded in the CRF and in the subject's source records. Investigators must record in the CRF their opinion concerning the relationship of the adverse event to a Janssen medicinal product.

All (serious and non-serious) adverse events reported for a Janssen medicinal product should be followed up in accordance with clinical practice.

SAEs, Adverse Events of Special Interest and Special Reporting Situations

All serious adverse events that have not resolved by the end of the study, or that have not resolved upon discontinuation of the subject's participation in the study, must be followed until any of the following occurs:

- The event resolves
- The event stabilizes
- The event returns to baseline, if a baseline value/status is available
- The event can be attributed to agents other than the study drug or to factors unrelated to study conduct

- It becomes unlikely that any additional information can be obtained (subject or health care practitioner refusal to provide additional information, lost to follow-up after demonstration of due diligence with follow-up efforts)

10.9. Pregnancy

All pregnancies or suspected pregnancies occurring in either a female subject or partner of a male subject are immediately reportable events and should be recorded on a Serious Adverse Event Report Form and be reported to Janssen Scientific Affairs, LLC **within 24 hours of becoming aware of the event..**

In the event of a pregnancy occurring in a female subject of childbearing potential or female partner of a male subject, Janssen will follow up with the clinical investigator each trimester of pregnancy and for 1 year following the birth of the infant (if applicable). Please reference the pregnancy information consent (permission) forms for data collection for additional information.

The exposure of any pregnant female (eg, caregiver or pharmacist) to Pomalidomide is also an immediately reportable event.

10.9.1. Females of Childbearing Potential:

Pregnancies and suspected pregnancies (including elevated beta human chorionic gonadotropin [β hCG] or positive pregnancy test regardless of age or disease state) of a female subject occurring while the subject is on study treatment, or within 28 days of the subject's last dose of POM or LD-Dex or within 3 months of last dose of Daratumumab, are considered immediately reportable events. Investigational product is to be discontinued immediately and the subject instructed to return any unused portion of the IP to the investigator. The pregnancy, suspected pregnancy, or positive pregnancy test must be reported to Janssen Drug Safety immediately by email, phone or facsimile, or other appropriate method, using the Initial Pregnancy Report Form, or approved equivalent form i.e. Clinical SAE Form. The female should be referred to an obstetrician-gynecologist, preferably one experienced in reproductive toxicity for further evaluation and counseling.

The investigator will follow the female subject until completion of the pregnancy and must notify Janssen Drug Safety immediately about the outcome of the pregnancy (either normal or abnormal outcome) using the Follow-up Pregnancy Report Form or approved equivalent form.

If the outcome of the pregnancy was abnormal (eg, spontaneous or therapeutic abortion), the investigator should report the abnormal outcome as an AE. If the abnormal outcome meets any of the serious criteria, it must be reported as an SAE to Janssen Drug Safety by facsimile, or other appropriate method, within 24 hours of the investigator's knowledge of the event using the SAE Report Form or approved equivalent form.

All neonatal deaths that occur within 28 days of birth should be reported, without regard to causality, as SAEs. In addition, any infant death after 28 days that the investigator suspects is related to the in utero exposure to the POM or LD-Dex or within 3 months of last dose of Daratumumab should also be reported to Janssen Drug Safety by facsimile, or other appropriate method, within 24 hours of the investigator's knowledge of the event using the SAE Report Form, or approved equivalent form.

10.9.2. Male Subjects

If a female partner of a male subject taking investigational product Pomalidomide, Daratumumab or Dexamethasone becomes pregnant, the male subject taking IPs (POM, DARA, or LD-Dex) should notify the investigator, and the pregnant female partner should be advised to call their healthcare provider immediately. Reports of pregnancy in a partner of a male subject should be recorded on a Serious Adverse Event Report Form and be reported to Janssen Scientific Affairs, LLC **within 24 hours of becoming aware of the event.**

10.10. Reporting of Serious Adverse Events

Any AE that meets any criterion for an SAE requires the completion of an SAE Report Form in addition to being recorded on the AE page/screen of the CRF. All SAEs must be reported to Janssen Drug Safety within 24 hours of the investigator's knowledge of the event by facsimile, or other appropriate method, using the SAE Report Form, or approved equivalent form. This instruction pertains to initial SAE reports as well as any follow-up reports.

Second primary malignancies will be monitored as events of interest and must be reported as serious adverse events. This includes any second primary malignancy, regardless of causal relationship to IP (POM, DARA, or LD-Dex), occurring at any time for the duration of the study, from the time of signing the ICD for at least 5 years from the date the last subject is randomized into the study. Events of second primary malignancy are to be reported using the SAE report form and must be considered an "Important Medical Event" if no other serious criteria apply; these events must also be documented in the appropriate page(s) of the CRF (ie, AE and SPM CRF) and subject's source documents. Documentation of the diagnosis of the SPM must be provided at the time of reporting as a serious adverse event (eg, any confirmatory histology or cytology results, x-rays, CT scans, etc.).

The investigator is required to ensure that the data on these forms is accurate and consistent.

This requirement applies to all SAEs (regardless of relationship to IPs [POM, DARA, or LD-Dex]) that occur during the study (from the time the subject signs informed consent to at least 30 days after the last dose of IPs [POM, DARA, or LD-Dex]), and those made known to the investigator at any time thereafter that are suspected of being related to IPs (POM, DARA, or LD-Dex). SAEs occurring prior to treatment will be captured.

The SAE report should provide a detailed description of the SAE and include summaries of hospital records and other relevant documents. If a subject died and an autopsy has been performed, copies of the autopsy report and death certificate are to be sent to Janssen Drug Safety as soon as these become available. Any follow-up data will be detailed in a subsequent SAE Report Form, or approved equivalent form, and sent to Janssen Drug Safety.

Where required by local legislation, the investigator is responsible for informing the Institutional Review Board (IRB)/Ethics Committee (EC) of the SAE and providing them with all relevant initial and follow-up information about the event. The investigator must keep copies of all SAE information on file including correspondence with Janssen and the IRB/EC.

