This is a multi-institution phase 1b/2 study of ATRA in combination with fixed dose Daratumumab, Pomalidomide and Dex for patients with relapsed multiple myeloma who have progressed on the combination of Dara + Len + Dex. During the dose escalation phase (phase 1b) and after the first cycle, patients who have not experienced a drug-limiting toxicity (DLT), have not shown signs of progressive disease (PD), and in the opinion of the investigator would continue to benefit from additional Dara + Pom + Dex + ATRA may receive additional cycles of treatment (see section 7.4 for details). The phase 2 portion will allow further enrollment at the maximum tolerated dose (MTD) to further evaluate safety and efficacy.

Study Population

Patients with relapsed or refractory multiple myeloma who have progressed on the combination of Dara + Len + Dex or Dara + Pom + Dex. We will include a maximum of 42 patients (among 20-32 subjects previously exposed to Dara + Len + Dex or 10-22 subjects previously exposed to Dara + Pom + Dex).

Length of Study

The overall study duration is expected to be three (3) years, two years for enrollment, one year to complete follow-up.

Treatment Plan

During 28-day treatment cycles, patients will receive Dara 1800 mg subcutaneous (SC) administration at their current dose upon enrollment onto the study depending on their cycle. (If they are on cycles 1-2

then they will receive Dara 1800 mg SC days 1,8,15,22; if they are on cycles 3-6 they will receive Dara 1800 mg SC days 1 and 15; if they are on cycle 7 or beyond they will receive Dara 1800 mg SC on day 1).

Pomalidomide will be administered at the patient's currently tolerated dose (4,3, or 2 mg po daily) on days 1-21. Patients who are progressing on daratumumab + lenalidomide + dexamethasone will start with the 4 mg dose (standard of care starting dose) of pomalidomide.

Dexamethasone will be administered at 40 mg once weekly on days 1,8,15 for patients 75 years old and younger and at 20 mg once weekly on days 1,8,15 for patients older than 75. Patients may stay on their currently administered steroid regimen if it does not match the above.

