For the Phase 1b portion, ATRA will be escalated as follows: 35.5 mg/m²/day, then 45mg/m²/day (see section 7.4 for details). The first administration of ATRA will be given in the morning, two days before the scheduled Dara infusion. The last administration of ATRA will be given in the evening of the day that Dara was administered (days -2, -1, and 0; day 0 is the day of Dara infusion).

Treatment repeats every 28 days for at least 8 cycles in the absence of disease progression or unacceptable toxicity. Patients achieving stable disease may continue to receive treatment in the absence of disease progression or unacceptable toxicity.

After completion of the study treatment, patients are followed up at 28 days and then every 3 months for up to 12 months. Subjects will be evaluated for disease response during each cycle and at the end of study.

Key Inclusion Criteria

1. Documented multiple myeloma with prior exposure to an immunomodulatory agent (IMiD), proteasome inhibitor (PI), and monoclonal antibody to CD-38 (CD-38 mo-Ab).
2. Patients must have 2 or more prior lines of therapy.
3. Patients must have been previously exposed to:
 - a. Dara+Len+Dex and must have achieved at least stable disease to this combination.
or;
 - b. Dara + Pom + Dex and must have achieved at least stable disease to this combination.
4. Histologically confirmed and relapsed multiple myeloma with measurable disease, defined by at least one of the following:
 - a. Serum monoclonal protein ≥ 0.5 g/dL;
 - b. Monoclonal protein in the urine on 24-hour electrophoresis ≥ 200 mg;
 - c. Serum immunoglobulin free light chain (FLC) ≥ 10 mg/dL (100 mg/L) provided serum FLC ratio is abnormal;
 - d. New or progressing biopsy proven plasmacytoma on exam or imaging; or
 - e. Bone marrow plasma cells $\geq 20\%$;
5. Cycle 1 day 1 of study treatment must be within 3 months of last exposure to Daratumumab.
6. Life expectancy >3 months

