All-trans retinoic acid (ATRA) has been shown in both cell lines and primary MM samples to increase CD38 expression levels and also to reduce expression of the complement-inhibitory proteins CD55 and CD59 (Nijhof et al, 2015). This resulted in significant enhancement of activity of Daratumumab in vitro and in humanized MM mouse models. Daratumumab and ATRA exhibit a strong synergy in MM cells derived from Dara-naïve patients and from patients with Dara-refractory disease, providing preclinical rationale for further evaluation of Daratumumab combined with ATRA in MM patients. Preliminary data from phase 1 trials combining Daratumumab and ATRA have shown that the combination is safe using ATRA 45 mg/m²/day dose.

Second primary malignancies will be monitored as events of interest and will be reported as a serious adverse event (SAE) regardless of causal relationship to investigational product (IP). The multicenter nature as well as the inclusion of patients in Japan of the study provides reassurance that the results are likely to have general applicability and the size of the study allows accurate description of the nature, frequency, and severity of the AE profile. Subjects will receive study treatment until PD or discontinuation. In studies evaluating agents for subjects with refractory MM or relapsed and refractory progressing or relapsed malignant diseases, it is common practice to continue study treatment until PD or intolerable toxicity develops. All subjects will be followed for OS, subsequent anti-myeloma therapies and SPMs.

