4.3. Study Duration

This study will consist of the following consecutive phases: Screening, Treatment and Follow-up.

The study will remain open to enrollment until the target subject enrollment of approximately 42 subjects has been reached. Given our current patient population we expect to complete enrollment in two years.

Each subject will be followed for up to 12 months after enrollment (unless the follow-up is shorter due to withdrawal of consent, loss to follow-up, or death).

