9.4. Safety analysis

All safety analyses will be performed on subjects who take at least one dose of study treatment and summarized using descriptive statistics. A separate listing and summary of all AEs and SAEs will be provided.

Please refer to Section 7.4 regarding stopping rules for dose-escalation during Phase 1b.

For phase 2, the first safety analysis will be performed 3 months after the first 10 patients are enrolled and the second safety analysis will be performed 3 months after the next 10 patients are enrolled.

A threshold of fatal AEs related to ATRA of <10% is proposed. Any rate of fatal events related to ATRA clearly in excess of this will result in stopping of the trial. For the 20 patients expected to be treated between phase 1b and phase 2 with one specific dose, this means that the cohort will be stopped if 1 or more fatal TEAEs occur during the first stage of phase 2, and 2 or more fatal TEAEs occur in both stages.

This trial will also be stopped if the rate of TEAE, Grade 4 events, in any non-hematologic system organ class (SOC) exceeds 10% with the exception of Grade 4 asymptomatic laboratory abnormalities. This trial will also be stopped if events meeting the criteria of a DLT occur with an incidence of >40% at any point. The stop will result in an immediate halt in enrollment and may also necessitate the halting of treatment of ongoing patients, depending on the nature and severity of the safety data by the investigators.

The All-Subjects-as-Treated (ASaT) population will be employed for safety analyses. The ASaT population consists of all subjects who received at least one dose of trial treatment. Subjects who entered the study and did not take any of the study drug(s) and had this confirmed, will not be evaluated for safety.

Descriptive tables that summarize the number and percentage of subjects that experience adverse events as categorized in the NCI CTCAE Version 5 will be generated:

The severity of the toxicities will be graded according to the NCI CTCAE v5 whenever possible.

Of note, a death from an unrelated and unforeseen circumstance (i.e. car accident) will not be counted toward toxicity for the stopping rules.

A grade 3 unexpected AE in the first patient will not stop enrollment in the arm

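### Section 10.10 promises at least 5 years of second primary malignancy capture after the last subject enters, but no scheduled follow-up reaches that far

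*Combined protocol and SAP*

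**What the plan says.** Section 10.10 gives SPMs special status: "Second primary malignancies will be monitored as events of interest and must be reported as serious adverse events". The duty applies regardless of causal relationship and runs "from the time of signing the ICD for at least 5 years from the date the last subject is randomized into the study". Section 4.2 adds: "All subjects will be followed for OS, subsequent anti-myeloma therapies and SPMs". It gives no length or schedule.

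The follow-up provisions are shorter, and they differ among themselves:

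- Section 4.3: "Each subject will be followed for up to 12 months after enrollment".
- Protocol Summary (Treatment Plan), 4.1 and 7.5: after study treatment is completed, "patients are followed up at 28 days and then every 3 months for up to 12 months". On treatment length: "Treatment repeats every 28 days for at least 8 cycles", absent progression or unacceptable toxicity.
- Protocol Summary (Length of Study): "The overall study duration is expected to be three (3) years, two years for enrollment, one year to complete follow-up".
- Section 5.2 ends general AE collection 30 days after treatment discontinuation. Sections 5.2 and 10.1 require SAEs to at least 30 days, and after that only SAEs that become known and are suspected to be related. Section 10.1 also contains a longer AE window, to the subject's last study-related procedure.
- Table 1 has a 3-monthly follow-up column, no row specific to SPMs, and no later visit.

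For analysis, Section 9.4 plans a listing and "Descriptive tables that summarize the number and percentage of subjects that experience adverse events". No person-time measure is described for any adverse event.

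**The concern.** SPMs are a late harm that the protocol itself singles out. A reader of 10.10 would take the reported SPM figure to reflect at least five years of surveillance of every surviving subject, whereas the scheduled contacts stop far earlier. A bare percentage of subjects gives no sign of this, because a subject seen for two months counts the same as one seen for two years. Section 4.2 strengthens the impression by saying that all subjects are followed for SPMs and that the study is large enough to describe the adverse-event profile accurately. What is at stake is how the absolute SPM frequency is ascertained and read.

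**Working it through.** **Calendar check.** Enrollment of 24 months plus 12 months of follow-up gives 36 months, which reproduces the stated 3 years and agrees with Section 4.3. The 10.10 window ends no earlier than month 24 + 60 = 84. A subject who stays alive therefore needs 60 months (last enrolled) to 84 months (first enrolled) of ascertainment. Against 12 months from enrollment, the shortfall is 48 to 72 months.

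The other follow-up rule gives 8 × 28 = 224 days of treatment, or 224/30.4375 = 7.4 months. Adding 12 gives 19.4 months. For the last subject enrolled this ends at month 24 + 19.4 = 43.4, already past the 36-month study length, so the follow-up rules also conflict with each other.

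**Person-time check.** Many subjects will die before 60 months, so the raw calendar gap overstates the loss. Inputs:

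- 42 subjects, the maximum in Section 4.1.
- Median overall survival 17.5 months, cited in Section 1 for daratumumab + pomalidomide + dexamethasone.
- Median 9 months, cited in Section 1 for disease resistant to bortezomib and lenalidomide, as a pessimistic bound.
- Assumptions of this review: exponential survival, uniform accrual over 24 months, no other loss.

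Person-years per subject observed for up to T years = (1 − exp(−λT))/λ, with λ = ln 2 / median in years. For 17.5 months, λ = 0.6931/1.4583 = 0.4753.

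- Rule A, 12 months from enrollment: T = 1, giving 0.796 per subject, or 33.4 in all.
- Rule B, 12 months after 8 completed cycles: T = 19.4/12, giving 1.127, or 47.3.
- Rule C, everyone observed to month 36: T uniform on 1 to 3 years, giving 1.260, or 52.9.
- Section 10.10 window: T uniform on 5 to 7 years, giving 1.978, or 83.1.

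Share of the 10.10 at-risk time covered:

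| Survival assumed | A | B | C |
|---|---|---|---|
| Median 9 months | 61% | 78% | 82% |
| Median 17.5 months | 40% | 57% | 64% |
| No deaths (limit) | 17% | 27% | 33% |

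Under rule A, medians of 12, 24 and 36 months give 51%, 34% and 28%. Across medians of 9 to 36 months and these rules, 18% (C, 9 months) to 72% (A, 36 months) of the at-risk time lies outside planned follow-up.

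**Expected events.** The documents give no SPM rate. At an assumed 1 to 4 per 100 patient-years and a 17.5-month median, rule A gives 0.3 to 1.3 expected events and the 10.10 window 0.8 to 3.3.

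**What zero events would mean.** With no SPM in 33.4 patient-years, the upper limit of the exact two-sided 95% interval is −ln(0.025)/33.4 = 3.689/33.4, or 11.0 per 100 patient-years. A table entry of 0% would not convey that.

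**The case against.** Several points on the other side are fair.

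- *The 12 months may start after treatment.* This stands, and it is why the result is given for three follow-up rules. Treatment beyond 8 cycles would narrow the gap further; earlier stopping would widen it. A reader might infer from Section 4.3 alone that the trial observes only about one year, or that 40% is the coverage. The other passages do not support that as the single figure.
- *There are other routes to capture.* Section 10.10 provides an SPM case report form, 10.4 lists other malignancies as an adverse event of special interest, and one sentence in 10.1 extends AE reporting to the last study-related procedure. The Table 1 row for AE/SAE review reads as continuous, and its span may have been lost in text extraction, so the absence of an SPM row does not prove that nothing is collected in follow-up. A reader might conclude that SPMs will be under-reported. That is an inference: the documents show only that late SPMs have no scheduled ascertainment.
- *The End of Trial definition in 4.4 could wait for late data.* It waits for data needed for pre-specified analyses, and no SPM analysis is specified.
- *SPM is not an objective or endpoint, and about one event is expected, so a listing is nearly enough.* Largely true: an interval would be wide, and Section 9.1 defers detail to a statistical analysis plan whose separate text is not available here. But the width is the information that a bare percentage hides, and patient-years cost little to report.
- *The wording looks inherited from another protocol.* Probably so, since 4.2 also describes countries outside the two listed US sites. It remains the operative text.

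**Conclusion.** The contradiction holds under every reading of the follow-up rules: an SPM duty running to at least month 84 cannot be met by scheduled contacts in a study expected to end at month 36. With a 17.5-month median survival, planned follow-up covers about 40% to 64% of the at-risk person-time in the stated window. The share is higher with shorter survival and lower with longer survival. These figures rest on exponential survival, uniform two-year accrual and no other loss; the contradiction needs none of those assumptions.

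A reader might go further and say that the five-year duty should simply be struck out. The documents do not settle which window is intended. Removing it would also leave SPMs arising more than 30 days after the last dose and not suspected to be related largely without a reporting duty, apart from the longer wording in 10.1.

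The point is worth correcting, but its reach is limited. There is no control arm, so only the absolute SPM description is affected. The response-rate endpoint, the dose-escalation rules and the stopping rules are untouched.

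**What to change.** 1. Reconcile Sections 10.10, 4.2, 4.3, 5.2 and 10.1 and the follow-up statements in the Protocol Summary, 4.1 and 7.5 to one SPM ascertainment window, with a contact schedule in Table 1 that reaches its end. Which window is right is for the sponsor and the investigators to decide. The same edit should settle whether the 12 months start at enrollment or at the end of treatment.
2. In 10.10, replace the reference to randomization with enrollment.
3. Add an explicit SPM question to the 3-monthly follow-up contacts already in Table 1.
4. In 9.4, report the SPM count with the patient-years observed, as a rate per 100 patient-years with an exact interval, counting follow-up to last contact. State that the trial does not estimate SPM risk beyond the follow-up performed, and bring the claim in 4.2 into line.

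The cost is protocol wording, one question per existing contact and one extra safety table. If the longer window is kept, later contacts must be added and resourced. If a shorter one is chosen, the stated surveillance claim becomes less favourable, and the reporting duty for later SPMs not suspected to be related must be addressed explicitly.
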